5.1. Product Characteristics

The revascularization device is designed with open loop structure. When the diameter of the stent changes with the diameter of the vessel, the stent pattern remains unchanged, only the size of the overlapping region in the circumferential direction changes. This design allows the thrombectomy stent to overlap in the vessel, increases the contact area with the thrombus, and can better capture the thrombus; meanwhile, the stent has the greatest support force at the beginning of deployment, and rapidly reduces the support force at the later stage of deployment, thus reducing the damage to the vascular intima; in addition, when withdrawn, the stent can maintain the screening area and reduce the risk of thrombus shedding during cutting. This design has excellent stent wall apposition, and will not separate from the thrombus when the stent is withdrawn, reducing the risk of thrombus shedding. Meanwhile, several precious metal developing wires are embedded in the stent, so that the outline of the stent can be clearly displayed under DSA device, ensuring the effectiveness and safety of the product in clinical use.

5.2. Device Composition, Operation Principle and Mechanism of

Action

5.2.1. Device Composition

[figure not shown]
The Ghunter Revascularization Device is composed of a thrombectomy stent, a push rod and an introducer sheath.

The thrombectomy stent is formed by laser engraving of nitinol material, with strong radial support force and excellent flexibility; the stent is connected distal to multiple radiopaque developing devices, so that the placement and deployment of the distal stent can be observed under DSA; multiple radiopaque wires are embedded on the main body of the stent, so that the deployment of the main body of the stent can be observed under DSA; the stent is also connected proximal to a radiopaque device, so that the relative position of the proximal stent and the distal microcatheter can be observed under DSA.

The push rod is fabricated with a specially processed wire to ensure sufficient push force is provided. It is subjected to multi-step mechanical processing and heat treatment while being composited with multiple materials, so that its distal end has good over-bending capacity while providing pushing force, for adapting to the complex intracranial vascular path.

The thrombectomy stent is retracted inside the introducer sheath during storage and transport, and during the operation, the introducer sheath is inserted into the proximal microcatheter, allowing the thrombectomy stent to be easily pushed into the inner lumen of the microcatheter and then into the target vessel.

The structure of revascularization device is as shown in the figure below:

5.2.2. Working Principle and Mechanism of Action

The revascularization device, by means of interventional therapy, delivers a metal thrombectomy stent into the intracranial target vessel. After fully deployed, the stent has a strong capacity to capture the thrombus, and then the thrombus is withdrawn to the outside body with the revascularization device to achieve the purpose of recanalization.

5.3. Study Scope

The revascularization device is intended to remove the thrombus from large intracranial blood vessels of ischemic stroke patients within 24 hours after symptom onset, so as to restore blood flow.

6. Overall Design

6.1. Study Design

6.1.1. Study Objective

To verify that the success rate of instant recanalization of Ghunter Revascularization Device is not inferior to Solitaire FR for endovascular treatment of acute ischemic stroke.

6.1.2. Selection of Study Method and Justification

The therapeutic effect and prognosis of AIS patients are related to whether the infarcted vessels can be opened in time. Therefore, whether the vessels are successfully opened will be the primary endpoint of the thrombectomy effect. This trial assumes that the recanalization success rate of the investigational product is not inferior to that of the control product, and this hypothesis will be verified by a sufficient sample size.

Study method: Prospective, multicenter, randomized controlled, non-inferiority test.

- 1) Prospective: research method that start from the present and track into the future is used.
- 2) Multicenter: More than 10 clinical sites are planned to be selected to conduct the clinical trial.
- 3) Randomized control: Randomization is performed using the Interactive Web Response System (IWRS), with competitive block randomization and competitive enrollment by each site. After signing the ICF and passing the screening, the subjects are randomized into the test group and control group in 1:1, with 110 each in the test group and control group. Randomization numbers and groups are distributed by randomization personnel in the randomization system of each site to avoid selection bias.
- 4) Non-inferiority test: to evaluate that the success rate of instant recanalization is not inferior to the control product when the investigational product is used for endovascular treatment of acute ischemic stroke.
- 5) Blind reading: The thrombectomy procedure will be burned on a CD in DICOM format, and the target vessel will be blindly evaluated for recanalization by a central interpretation room independent of the trial.

6.1.3. Measures to Reduce and Avoid Bias

6.1.3.1. Multicenter:

The samples from multi sites are more representative than those from a single site, and the latter may lead to bias of study results due to its systematic errors. Therefore, the conclusion obtained can be more reliable. In order to reduce

differences in procedures between sites, trainings of study personnel in each site on the use of the same standards in the study should be performed. Clear evaluation criteria are adopted for effectiveness and safety indicators.

6.1.3.2. Investigator Training:

Before the start of the clinical trial, the CRA shall coordinate with the director of the study sites to train the investigators on the trial protocol so that the investigators can understand and be familiar with the test products, and shall also grasp all new information related to this product found during the trial.

6.1.3.3. Monitoring of Clinical Trial:

The monitoring plan is developed and the CRA appointed by the sponsor shall conduct regularly on-site monitoring visit to the hospitals conducting the clinical trial to ensure that all the contents in the trial protocol are strictly observed and the EDC is checked to ensure consistency with the raw data.

6.1.3.4. Management of Clinical Trial:

A clinical research coordinator (CRC) will assist the investigator in performing the specific non-medical judgment affairs of the clinical trial to ensure that all aspects of the trial protocol are strictly adhered to and that the EDC data is consistent with the raw data.

[figure not shown]
6.1.4. Investigational Medical Device and Control Device/Control Diagnostic and Therapeutic Method

6.1.4.1. Investigational Product:

Product name: Ghunter Revascularization Device

Models: ISR3-20, ISR3-25, ISR3-30, ISR4-20, ISR4-30, ISR4-40, ISR6-20, ISR6-30, ISR6-40

The naming rule of Ghunter revascularization device is ISR XYY, and each letter represents the meaning as follows:

According to the target vessel diameter and thrombus length, the revascularization device is divided into the following specifications:

Model	Recommended vessel diameter ¹		Compatible microcatheter minimum ID		Diameter × effective length ²	Total length of thrombectomy stent	Total length of revascularization device	Distance from proximal marker to distal radiopaque marker	Quantity of radiopaque markers	
	Minimum (mm)	Maximum (mm)	(mm)	(inch)	(mm×mm)	(mm)	(cm)	(cm)	Distal	Proximal
ISR3-20	1.5	3.0	0.43	0.017	3×20	31	200	<130	3	1
ISR3-25	1.5	3.0	0.43	0.017	3×30	36	200	<130	3	1
ISR3-30	1.5	3.0	0.43	0.017	3×40	41	200	<130	3	1
ISR4-20	2.0	4.0	0.53	0.021	4×20	31	200	<130	3	1
ISR4-30	2.0	4.0	0.53	0.021	4×30	41	200	<130	3	1
ISR4-40	2.0	4.0	0.53	0.021	4×40	51	200	<130	3	1
ISR6-20	3.0	5.5	0.69	0.027	6×20	31	200	<130	4	1
ISR6-30	3.0	5.5	0.69	0.027	6×30	41	200	<130	4	1
ISR6-40	3.0	5.5	0.69	0.027	6×40	51	200	<130	4	1

1. XX revascularization device is selected based on the minimal diameter, listed in Table 1, of the thrombus-located vessel.
2. The effective length of XX revascularization device should be no less than the thrombus length.

Manufacturer: Sinomed Neurovita Technology Inc.

6.1.4.2. Control Product:

Product name: Solitaire FR

Specification/model (mm × mm): 4 × 15, 4 × 20, 6 × 20, 6 × 30

Manufacturer: Covidien Healthcare International Trading (Shanghai) Co., Ltd.

6.1.5. Subject Enrollment

6.1.5.1. Inclusion Criteria

General inclusion criteria:

- 1) ≥ 18 years old;
- 2) NIHSS ≥ 6 at randomization;
- 3) Pre-onset mRS < 2;
- 4) Acute ischemic stroke was diagnosed;
- 5) Within 24h from the stroke onset to the completion of femoral artery puncture (regardless of whether intravenous thrombolysis has been performed); the time point of stroke onset is defined as the time point at which the patient is last known to be normal;
- 6) The subject (or his/her guardian) agrees to participate in this study and signs

the informed consent form (ICF).

Angiographic inclusion criteria:

- 1) Cerebral CT or MR should be performed when the time from the stroke onset to the completion of femoral artery puncture of a patient is ≤ 6 h;
- 2) Cerebral CT or MR should be performed when the time from the stroke onset to the completion of femoral artery puncture of a patient is 6 (exclusive)-24h (inclusive), and his/her ASPECTS score should be ≥ 6 . (If immediate CT perfusion imaging or MR perfusion imaging is feasible, it is recommended to perform CTP or MRP simultaneously to assist in the assessment of the infarct core, and his/her ASPECTS score should also be ≥ 6);
- 3) DSA angiography shows acute occlusion of large intracranial arteries, including intracranial internal carotid artery (C4-C7), middle cerebral artery (M1/M2), basilar artery and intracranial vertebral artery (V4).

6.1.5.2. Exclusion criteria

General exclusion criteria:

- 1) Those who could undergo neither MRI nor CT;
- 2) Those with hemorrhagic stroke or major ischemic stroke within 6 months before enrollment;
- 3) Those with severe persistent hypertension that could not be controlled by intravenous injection for blood pressure reduction, i.e. patients with sustained SBP > 185 mmHg or sustained DBP > 110 mmHg;
- 4) Those with presumed septic emboli or suspected bacterial endocarditis;
- 5) Renal failure, defined as creatinine > 3.0 mg/dL ($264 \mu\text{mol/L}$);
- 6) Those with blood glucose < 2.78 mmol/L (50 mg/dL) or > 22.20 mmol/L (400 mg/dL);
- 7) Decreased platelet count ($< 40 \times 10^9/\text{L}$);
- 8) Those with known hemorrhage tendency, coagulation factor deficiency, are taking anticoagulants and with INR > 3.0 ;
- 9) Pregnant or lactating women;
- 10) Those with known severe allergy to contrast media or known allergy to nickel materials;
- 11) Those with disorders possessing possibility of affecting neurological assessment (e.g., neurological and psychiatric disorders);
- 12) Those with heart, lung, liver failure or other serious disorders leading to disablement of interventional operation;

- 13) Participating in clinical trials of other drugs or devices;
- 14) Life expectancy less than 6 months;
- 15) Other conditions judged by the investigator to be not suitable for inclusion.

Angiographic exclusion criteria:

- 1) There is evidence of intracranial hemorrhage on CT or MR or known hemorrhage tendency;
- 2) CT/MR/DSA angiography suggests > 1 vascular occlusion (e.g., simultaneous occlusion of bilateral internal carotid artery vessels, or simultaneous occlusion of intracranial vessels in anterior and posterior circulation, or simultaneous occlusion of intracranial and extracranial internal carotid artery);
- 3) Those with carotid artery dissection, occlusion of the initial segment of the carotid artery or arteritis;
- 4) Those whose access vessels are quite tortuous, making the revascularization device difficult to reach the target location.

6.1.5.3. Criteria and Procedures for Withdrawal from/Discontinuation of Trial Treatment

The subjects may withdraw from the study at any time during the course of the study without giving a reason: moreover, subjects may choose not to undergo any study procedures after signing the ICF, and if subjects choose not to undergo any study procedures after signing the ICF, the investigator must be informed. However, subjects have the right to continue receiving the standard of care regardless of the cases.

Any subject may also be withdrawn from the study by the investigator based on medical judgement.

Subject's premature discontinuation or withdrawal from the study can be any of the following cases, but not limited to:

- 1) The subject is unwilling to continue participating in this study for any reason;
- 2) For medical or safety reasons, the investigator believes that the subject should be withdrawn from the study;
- 3) Serious protocol violation (confirmed by the principal investigator);
- 4) The investigator or the sponsor requests to terminate the study for any reason;
or
- 5) Death.

For all subjects who terminate the study early, the investigator should make every effort to find out the reasons for withdrawal from the trial, for example: adverse

events, failure of corrective treatment, the investigator's decision or other reasons. The reasons for withdrawal should be recorded in the EDC. Subjects who withdraw early should be requested to complete an early withdrawal visit according to the visit schedule.

Subjects who withdraw from the study will not be replaced, i.e. the randomization number will be uniquely related to each subject and cannot be reused.

6.1.5.4. Expected Overall Duration of Clinical Trial and Its Rationale

Overall duration: About 30 months.

The overall duration of the clinical study includes the time of obtaining EC approval letters from all the study hospitals, time of signing the clinical study agreement, filling time, time of study initiation, enrollment and follow-up of subjects, time of collection and statistics of study data, and summary report writing, etc. The expectation is from March 2021 to September 2023.

Rationale: The overall duration of this trial is predicted based on the number of the investigational devices used for the cases in each hospital to ensure adequate source of cases for the study, as well as the patient follow-up schedule and the process systems of each hospital.

6.1.5.5. Expected Duration of Participation for Each Subject

The duration of each subject participation is defined as a period from the time that the patient signs the ICF to the end time of the final follow-up. According to the study design, the visit time of each subject: screening/baseline period (-1 d~0 d preoperatively), treatment period (day of operation/0d), observation period (24 ± 12 h postoperatively), follow-up period (7 ± 2 d postoperatively (before discharge in case of premature discharge)), and follow-up period (90 ± 14 d postoperatively). Therefore, the expected duration of participation of each subject is around 90 days.

6.1.5.6. Number of Subjects for Confirmatory Clinic Trial

220 subjects are enrolled into this clinical study in total.

6.1.6. Effectiveness Evaluation Methods

- 1) Description of effectiveness endpoints
 - a) Primary effectiveness endpoint: success rate of instant recanalization
 - b) Secondary effectiveness indicators: Proportion of subjects with mRS scores of 0-2 on 90d postoperatively, time from femoral artery puncture to recanalization/the end time of operation for subjects whose recanalization failed, proportion of subjects with NIHSS score decrease > 4 , and success rate of device operation
- 2) Selection of Method and Time to Evaluate, Record and Analyze Effectiveness

Indicators

Primary endpoint:

● Success rate of instant recanalization

Recording time and method: During thrombectomy, cerebral vascular DSA examination will be performed to analyze whether the recanalization success is achieved. If the recanalization is affected due to in situ atherosclerotic stenosis, vascular dissection and vasospasm after thrombectomy, the investigator can handle it in an appropriate way and determine whether the target vessel is successfully revascularized according to the recanalization after treatment.

* Recanalization success was evaluated separately by clinicians and a central interpretation room independent of the study, and when the evaluation results were inconsistent, the results of the blind evaluation by the central interpretation room prevailed.

Formula: Success rate of instant recanalization = Number of subjects with instant recanalization success in this group/Number of subjects treated with revascularization devices in this group $\times 100\%$.

Criteria for instant recanalization success: target vessel recanalization, with mTICI grade of 2b or 3. The mTICI grading is shown in Appendix 3.

Secondary endpoint:

● Proportion of mRS scores of 0-2

Recording time and method: preoperatively and 90 ± 14 d postoperatively. Postoperative subjects' degree of disability will be analyzed by 90-d mRS scores postoperatively. The mRS score is based on mRS scale (as shown in Appendix 4).

Proportion of subjects with mRS scores of 0-2 = Subjects with mRS scores of 0-2 on 90d postoperatively/Number of subjects treated with intracranial thrombectomy device $\times 100\%$.

● Time from femoral artery puncture to recanalization/the end time of operation for patients whose recanalization failed

Evaluation time: Intraoperatively

Evaluation site: target vessel

Evaluation method: The recanalization time will be judged by intraoperative procedure and the vascular condition shown by imaging.

Formula: Recanalization time = Recanalization success time - Femoral artery puncture time

Precautions: The recanalization time is the time from the completion of femoral

artery puncture to recanalization success. If the vessel is not revascularized, the end time point is recorded as the time point at the end of operation. Criterion for instant recanalization success: target vessel recanalization with mTICI grade of 2b or 3 after thrombectomy with the investigational device. The investigator's judgment intraoperatively shall prevail.

- **Proportion of subjects with NIHSS score decrease > 4**

Recording time and method: The preoperative and postoperative NIHSS scores are compared by three time points: pre-operation, 24 ± 12 h postoperatively and 7 ± 2 d postoperatively (before discharge in case of premature discharge) to analyze the degree of impairment and improvement of neurological functions preoperatively and postoperatively. The NIHSS score is the total score based on NIHSS scale (as shown in Appendix 5).

Proportion of subjects with NIHSS score decrease > 4 = Number of subjects with NIHSS score decrease > 4 postoperatively in this group/Number of subjects treated with thrombectomy through stents in this group $\times 100\%$.

- **Success rate of device operation**

Definition: The success rate of device operation is the proportion of device operation success. Device operation success is defined as successful delivery of the investigational device to the diseased vessel site to complete accurate deployment and withdrawal.

Evaluation time: Intraoperatively (evaluation endpoint)

Evaluation site: target vessel

Evaluation method: The success rate of device operation is calculated by intraoperative evaluation of whether the delivery, deployment and withdrawal of the thrombectomy device are completed.

Formula: Device operation success = Number of devices delivered, deployed and withdrawn/Number of all investigational devices used in this group $\times 100\%$.

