6.2.1.3. Visit Schedule

1) Visit 1: Screening/baseline period (-1 d ~ 0 d)

After all the subjects (or their guardians) sign the ICF, the investigator will screen the subjects according to the inclusion/exclusion criteria of the study. During this period, the following visit contents need to be completed:

- i. Signing of ICF;
- ii. Recording of basic information of the subject;
- iii. Present medical history: onset time and admission time;
- iv. Medical history: history of allergy, history of stroke, history of other significant diseases (e.g., presumed septic emboli or suspected bacterial endocarditis), history of neurological diseases;
- v. Vital signs (blood pressure, heart rate);
- vi. NIHSS score;
- vii. MRS score, ASPECTS score (required within 6 - 24 h of onset);

Laboratory examination:

- viii. Pregnancy testing (Only for women of childbearing potential who are planning to become pregnant)
- ix. Administration of anticoagulant and antiplatelet drugs;
- x. Cerebral CT or MR will be performed, and the following information will be recorded:
 - a) When the onset time is ≤ 6 h, cerebral CT or MR is performed;
 - b) Cerebral CT or MR is performed when the onset time is 6 (exclusive)-24h (inclusive) to determine whether ASPECTS score ≥ 6 is met; (if immediate CT perfusion imaging or MR perfusion imaging is feasible, CTP or MRP is recommended to assist in the assessment of the infarct

core to determine whether ASPECTS score ≥ 6 is met).

* For laboratory tests and imaging tests, the results after this admission and the results of external hospital examinations within 24h preoperatively are acceptable.

c) Other significant abnormal conditions.

2) Visit 2 (0 d):

i. Recording of cerebral vascular DSA:

- a) Name of target vessel and lesion segment, proximal diameter of occluded vessel
- b) mTICI image grading postoperatively
- c) Does the patient suffer from carotid origin occlusion or carotid dissection or arteritis?
- d) Is the vessel access so tortuous that makes it difficult for the investigational/control device to reach the target location?

ii. Recording of the operations:

- a) Date of operation, femoral artery puncture time, operation start and recanalization time (or end time)
- b) Intraoperative treatment method (Are implant stent, balloon dilatation and antithrombotic drugs used)

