- c) Model of each revascularization device, the frequency of thrombectomy procedure, evaluation of success rate of device operation, whether the vessel is successfully revascularized, recanalization success time, and reason for failure

iii. Administration of anticoagulant and antiplatelet drugs;

iv. Recording of adverse events;

v. Recording of device defects:

Note: The frequency of thrombectomy procedure with the thrombectomy device will be determined by the investigator on a case-by-case basis. If recanalization fails, the investigator may use other diagnostic and therapeutic measures (including but not limited to dual-stent technique, stent implantation, and aspiration device) according to specific case characteristics.

3) Visit 3: Observation period (V3: 24 ± 12 h postoperatively)

The subjects undergo clinical follow-up $24 \text{ h} \pm 12 \text{ h}$ postoperatively. All the visit information will be analyzed and recorded by investigators. In this visit, the following visit contents need to be completed:

- i. Vital signs;
- ii. NIHSS score;
- iii. Laboratory tests;
- iv. Cerebral CT or MR will be performed, and the following information will be recorded:
 - a) Is there intracranial hemorrhage (parenchymal hematoma, subarachnoid hemorrhage, ventricular hemorrhage)
 - b) Is there is a new cerebral infarction
 - c) Other significant abnormal conditions
- v. Administration of anticoagulant and antiplatelet drugs;
- vi. Recording of adverse events;
- 4) Visit 4: Follow-up period (V4: 7 ± 2 d postoperatively (before discharge in case of premature discharge))

The subjects undergo clinical follow-up 7 ± 2 d postoperatively. All the visit information will be analyzed and recorded by investigators. In this follow-up visit, the following visit contents need to be completed:

- i. Vital signs;
- ii. NIHSS score;
- iii. Laboratory tests (if laboratory test results had already been collected at Visit 3, they might not be collected here);
- iv. Administration of anticoagulant and antiplatelet drugs;
- v. Recording of adverse events;
- 5) Visit 5: Follow-up period (V5: 90 ± 14 d postoperatively)

[figure not shown]
The subjects undergo outpatient/telephone follow-up 90 ± 14 d postoperatively. All the visit information will be analyzed and recorded by investigators. In this follow-up visit, the following visit contents need to be completed:

- i. mRS score;
- ii. Administration of anticoagulant and antiplatelet drugs;
- iii. Recording of adverse events;

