2.1. Efficacy Endpoints

2.1.1. Primary efficacy endpoint

Success rate of immediate recanalization.

Vascular recanalization success: Target vessel recanalization with mTICI grade 2b or 3.

Success rate of immediate recanalization = Number of subjects in this group with immediate recanalization success / Number of subjects in this group undergoing intracranial thrombectomy with stenting $\times 100\%$.

Vascular recanalization success is assessed independently by both the treating clinician and a central reading laboratory. In case of disagreement, the blinded assessment by the central reading laboratory prevails.

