6.5. Surgical Record (FAS)

Table21 Target Vessel Surgery Information

Item	Indicator	Experimental Group	Control Group	Total
Number of Target Vessels*	1 n(%)			
	2 n(%)			
	Total (Missing)			
	Statistic			
	P-value			
Number of devices used	1 n(%)			
	2 n (%)			
	Total (Missing)			
	Statistic			
	P-value			

Item	Indicator	Experimental Group	Control Group	Total
Number of Thrombectomy Procedures	N(Missing)			
	Mean (SD)			
	Median			
	Q1, Q3			
	Min,Max			
	Statistic			
	P-value			
Number of Thrombectomy Procedures - Qualitative	1 time n(%)			
	2 times n(%)			
	≥3 times n(%)			
	Total (Missing)			
	Statistic			
	P-value			
Distal Embolism	Yes n(%)			
	No n(%)			
	Total (Missing)			
	Statistic			
	P-value			
Whether underlying stenosis was detected after recanalization	Yes n(%)			
	No n(%)			
	Total (Missing)			
	Statistic			
	P-value			
Use of Recute or Other Auxiliary Therapy	Yes n(%)			
	No n(%)			
	Total (Missing)			
	Statistic			
	P-value			
Stent implantation for recute treatment	Yes n(%)			
	No n(%)			
	Total (Missing)			
	Statistic			
	P-value			
Use of Balloon Dilatation for Recute Treatment	Yes n(%)			
	No n(%)			
	Total (Missing)			
	Statistic			
	P-value			
Other Recute Treatments Used	Yes n(%)			
	No n(%)			
	Total (Missing)			

Item	Indicator	Experimental Group	Control Group	Total
	Statistic			
	P-value			

Note: Except for analyses where the number of target vessels is the subject unit, all other analyses in this table use target vessel units.

Table22 Thrombectomy Device Usage Information (Device Units)

Item	Indicator	Experimental Group	Control Group	Total
Stent Diameter (mm)	N(Missing)			
	Mean(SD)			
	Median			
	Q1, Q3			
	Min,Max			
	Statistic			
	P-value			
Stent Length (mm)	N(Missing)			
	Mean(SD)			
	Median			
	Q1, Q3			
	Min,Max			
	Statistic			
	P-value			
Device Specifications (Diameter × Length) (mm × mm)	3×20 n(%)			
	3×30 n(%)			
	3×40 n(%)			
	4×15 n(%)			
	4×20 n(%)			
	4×30 n(%)			
	4×40 n(%)			
	6×20 n(%)			
	6×30 n(%)			
	6×40 n(%)			
	Total (Missing)			
	Statistic			
	P-value			

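### The primary endpoint is scored after treatment other than the assigned device, its definition conflicts with the one used for recanalization time, and no device-only analysis is planned to support the device claim

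*Protocol*

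**What the plan says.** The objective in Protocol 3.1 and 6.1.1 is a comparison of two devices: Ghunter's instant recanalization rate against that of Solitaire FR.

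**Primary endpoint, Protocol 6.1.6.** The criterion carries no device qualifier: "Criteria for instant recanalization success: target vessel recanalization, with mTICI grade of 2b or 3". For three vessel conditions the scoring point is explicit: "If the recanalization is affected due to in situ atherosclerotic stenosis, vascular dissection and vasospasm after thrombectomy, the investigator can handle it", and the investigator is then to "determine whether the target vessel is successfully revascularized according to the recanalization after treatment". When the clinician and the central reader disagree, the blinded central reading prevails.

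**Other treatment, Protocol 6.2.1.3, Visit 2.** "If recanalization fails, the investigator may use other diagnostic and therapeutic measures (including but not limited to dual-stent technique, stent implantation, and aspiration device". Nothing there says how a subject treated in this way counts for the primary endpoint. The only outcome grading in the Visit 2 list is "mTICI image grading postoperatively".

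**SAP.** Section 2.1.1 has "Vascular recanalization success: Target vessel recanalization with mTICI grade 2b or 3" and does not mention rescue; nor does 5.4.1. Table 23 tabulates the immediate postoperative grade.

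**Recanalization time, Protocol 6.1.6.** Here instant recanalization success means "target vessel recanalization with mTICI grade of 2b or 3 after thrombectomy with the investigational device". SAP 2.1.2 carries the same restriction.

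**Rescue data.** SAP Table 21 has a row "Use of Recute or Other Auxiliary Therapy", with rows for stent, balloon and other treatment, compared by arm. Neither document plans a device-only analysis or one that counts rescue as failure.

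**The concern.** The same success concept has two definitions. A vessel that reaches 2b/3 only after, say, balloon dilatation of a stenosis is a success on the primary endpoint but not, as written, on the time endpoint.

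The direction matters in a non-inferiority trial. Treatment available in both arms raises both rates and pulls the difference towards zero, so a real device deficit can be hidden. The operator receives the allocation before treating (Protocol 6.2.1.2), so the choice to treat further is made with the arm known. Blinded reading does not remove the dilution if the image graded is the final one.

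At stake is what a pass under Protocol 8.2 would mean: that the device met the margin, or that the device together with whatever followed it did.

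**Working it through.** **Plan's own figure.** From Protocol 7.2.1: 89% in both arms, margin 12.5 points, one-sided α 0.025, power 80%.

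n = (1.960 + 0.842)² × 2 × 0.89 × 0.11 / 0.125² = 98.36, so 99 per arm. 99 / 0.9 = 110 per arm, 220 in total. The stated sample size reproduces.

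**Effect on the difference.** Let qT and qC be the device-only failure rates, and rT and rC the shares of failures converted by other treatment.

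- Observed difference = -[qT(1-rT) - qC(1-rC)].
- With rT = rC = r, this is (1-r) × the device-only difference.
- If the shares differ, the deficit still shrinks unless rC × qC exceeds rT × qT. With 11% and 23.5% failures, rC would have to exceed 0.235/0.11 = 2.1 times rT for the direction to reverse.

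**Chance of declaring non-inferiority when the device-only difference is exactly -12.5 points.** The documents give no r, so it is assumed over a range. Two readings of the 89% are possible:

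- A: 89% is the device-alone control rate. Scored rates are control 1 - 0.11(1-r), test 1 - 0.235(1-r).
- B: 89% is the scored control rate after all treatment. Scored rates are control 0.89, test 0.89 - 0.125(1-r).

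Exact binomial enumeration, 110 per arm, Wald 95% interval, lower limit above -12.5%:

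| r | Observed difference (points) | A | B |
|---|---|---|---|
| 0 | -12.5 | 2.8% | 2.8% |
| 10% | -11.25 | 5.0% | 4.8% |
| 25% | -9.4 | 11.4% | 10.1% |
| 50% | -6.25 | 39.8% | 27.9% |

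With 99 per arm the r = 50% row becomes 37.9% (A) and 25.3% (B). With a score interval at 110 per arm, reading A gives 9.5% at r = 25% and 33.4% at r = 50%.

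**Power of a device-only analysis if 89% already includes rescue.** Device-only rate = 1 - 0.11/(1-r). Power is by normal approximation at 99 per arm.

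| r | Device-only rate | Power | n per arm for 80% (total after 10% dropout) |
|---|---|---|---|
| 10% | 87.8% | 77% | 108 (240) |
| 25% | 85.3% | 70% | 126 (280) |
| 50% | 78.0% | 56% | 173 (386) |

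If 89% is already a device-only rate, 99 per arm stands.

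**The case against.** Several arguments limit the point.

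- A reader might infer that every failure of the assigned device is scored a success once rescued. The documents support that only for stenosis, dissection and vasospasm. The wider list in 6.2.1.3 begins once recanalization has failed, the endpoint is called instant and assessed during thrombectomy, and a reason for failure is recorded. Counting those subjects as failures is a possible reading. This stands: for them the defect is silence, although unqualified postoperative grading points towards success.
- The size rests on an assumed r. Shares of 50% or more would probably need the wider rescue to count as success. This stands, which is why small shares are shown too.
- Protocol 7.2.1 describes the 89% as a rate after treatment, which favours reading B and its smaller figures. This stands as far as it goes; the text does not say whether that means treatment with the device or all treatment.
- Final mTICI is a legitimate endpoint for a treatment strategy, and a -6.25 point difference on it lies inside the margin. True, but the objective names the device, and the plan never says it tests a strategy.
- Blinded central reading and the comparison of rescue use by arm are partial safeguards. They could expose unequal rescue; they do not settle which image is scored.
- Counting every stent or balloon case as failure would be wrong for vessels already at 2b/3 after the device. Table 21 expects stenosis found after recanalization. If 10% of successes in each arm were reclassified in this way, -12.5 would become -11.25 points and the pass rate 4.2%. This stands and shapes the fix.

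**Conclusion.** The point holds as a conflict of definitions with a known direction and an unknown size. Post-treatment scoring is explicit for three conditions and unstated for other rescue, and it conflicts with the device-specific definition used for recanalization time (taking the investigational device there to mean the assigned device in either arm).

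Under equal conversion, the device difference shrinks by the factor (1-r). For a device exactly at the margin, the chance of passing rises from about 3% to about 5% (r=10%), 10-11% (r=25%) or 28-40% (r=50%). These are error rates for the device-only question, they depend on an assumed r, and equal conversion is itself an assumption.

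The documents do not support the stronger conclusion that the sample size is wrong or that the primary endpoint must be replaced. Replacement is a trade-off that costs power. What the plan lacks is a clear definition and a pre-specified analysis that can answer the device question.

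**What to change.** 1. Reconcile the primary and time-endpoint definitions in Protocol 6.1.6, the Visit 2 note in 6.2.1.3, and SAP 2.1.1 and 2.1.2. State whether the primary endpoint, the 89% and the 12.5% margin refer to device-only or post-treatment recanalization, and how subjects rescued after failed recanalization are scored.
2. In SAP 5.4.1, pre-specify a supportive non-inferiority analysis at -12.5%, in FAS and PPS, on the blinded core-laboratory mTICI after the last pass of the assigned device and before any other treatment.
3. Where that image cannot be graded, count a subject rescued after failed recanalization as a non-success. Do not count as failure a vessel already at 2b/3 before adjunct treatment.
4. Report this beside the primary result with rescue use by arm, and limit any device-level claim if the two disagree.

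**Cost.** Wording changes, one more core-laboratory grade from procedural DSA that already goes to the central reader, and one more results table. Table 21 alone is not enough: it has no separate aspiration or dual-stent row, does not time the rescue against the mTICI grade, and counts target vessels. The supportive analysis may fall short of 80% power: about 77% at r=10% and 70% at r=25% with 99 per arm, if the 89% includes rescue. Operators' freedom to treat is unchanged.
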